5.2.8. Standard Derivations and Reporting Conventions

The following conversion factors will be used to convert days into weeks, months or years: 1 week = 7 days, 1 month = 30.4375 days, 1 year = 365.25 days.

Demographics and physical measurements:

- Age [years]:

(date of given informed consent - date of birth + 1) / 365.25

In case of missing day, day only: Age [years]: (year/month of given informed consent – year/month of birth)

In case only year of birth is given: Age [years]: (year of given informed consent - year of birth)

The integer part of the calculated age will be used for reporting purposes.

$BMI (kg/m^2) = weight (kg) / [height (m)]^2$

For reporting conventions, mean and median should generally be displayed one more decimal place than the raw data and standard deviation should be displayed to two more decimal places than the raw data. Percentages will be reported to one decimal place. The rounding will be performed to closest integer/first decimal using the common mid-point between the two consecutive values. Eg, 5.1 to 5.4 will be rounded to an integer of 5, and 5.5 to 5.9 will be rounded to an integer of 6.

5.2.9. Unscheduled Visits

Generally, data collected at unscheduled visits will be included and analyzed for both safety and efficacy analyses in the same fashion as the data collected at scheduled visits except where otherwise noted in the sections that follow. Descriptive statistics (mean, SD, median, minimum, maximum, quartiles) by nominal visit or time point for safety endpoints such as laboratory measurements, ECGs and vital signs will include only data from scheduled visits.

5.2.10. Adequate Baseline Tumor Assessment

Adequate baseline is defined using the following criteria:

All baseline assessments must be within 31 days prior to and including date of first dose of study treatment.

All documented lesions must have non-missing assessments (ie, non-missing measurements for target lesions and non-missing lesions assessment status at baseline for non-target lesions).

5.2.11. Adequate Post-baseline Tumor Assessment

An adequate post-baseline assessment is defined as an assessment where a response of CR, PR, SD, non-CR/non-PD, or PD can be determined (see [Section 6.2.1.1](#)). Time points where the response is not evaluable (NE) or no assessment was performed will not be used for determining the censoring date.

5.3. Methods to Manage Missing Data

5.3.1. Missing Data

Unless otherwise specified, all data will be evaluated as observed, and no imputation method for missing values will be used.

In all patient data listings imputed values will be presented. In all listings imputed information will be flagged.

Missing statistics, eg, when they cannot be calculated, should be presented as 'ND' or 'NA'. For example, if N=1, the measure of variability (SD) cannot be computed and should be presented as 'ND' or 'NA'.

5.3.1.1. Pharmacokinetic Concentrations

Concentrations Below the Limit of Quantification

For all calculations, figures and estimation of individual pharmacokinetic parameters, all concentrations assayed as below the level of quantification (BLQ) will be set to zero. In log-linear plots these values will not be represented. The BLQ values will be excluded from calculations of geometric means and their CIs. A statement similar to ‘All values reported as BLQ have been replaced with zero’ should be included as a footnote to the appropriate tables and figures.

Deviations, Missing Concentrations and Anomalous Values

In summary tables and plots of median profiles, concentrations will be set to missing if one of the following cases is true:

1. A concentration has been reported as ND (ie, not done) or NS (ie, no sample);
2. A deviation in sampling time is of sufficient concern or a concentration has been flagged as anomalous by the clinical pharmacologist.

All the concentration data will be listed but the summaries of C_{trough} and C_{max} , will not include concentrations associated with samples collected more than 20% before or after the planned time. Summary statistics will not be presented at a particular time point if more than 50% of the data are missing. For analysis of pharmacokinetic concentrations, no values will be imputed for missing data.

5.3.1.2. Pharmacokinetic Parameters

If a PK parameter cannot be derived from a patient’s concentration data, the parameter will be coded as NC (ie, not calculated). NC values will not be generated beyond the day that a patient discontinues.

In summary tables, statistics will be calculated by setting NC values to missing. Statistics will not be presented for a particular treatment if more than 50% of the data are NC. For statistical analyses (ie, analysis of variance), PK parameters coded as NC will also be set to missing.

If an individual patient has a known biased estimate of a PK parameter (due for example to a deviation from the assigned dose level), this will be footnoted in summary tables and will not be included in the calculation of summary statistics or statistical analyses.

5.3.2. Handling of Incomplete Dates

5.3.2.1. Disease History

Incomplete dates for disease history (eg, initial diagnosis date, date of documented, locally advanced, inoperable or metastatic disease diagnosis, date of response or progression in prior treatment) will be imputed as follows:

- If the day is missing, it will be imputed to the 15th day of the month.
- If both day and month are missing and the year is prior to the year of the first study treatment, the month and day will be imputed as July 1st.
- If both day and month are missing and the year is same as the year of the first study treatment, the month and day will be imputed as January 1st.
- If the date is completely missing, no imputation will be performed.

5.3.2.2. Adverse Events

Incomplete AE-related dates will be imputed as follows:

- If the AE onset date is missing completely, then the onset date will be replaced by the start of study treatment.
- If only the day part of the AE onset date is missing, but the month and year are equal to the start of study treatment, then the AE onset date will be replaced by the start of study treatment. For example, if the AE onset date is --/JAN/2015, and study treatment start date is 15/JAN/2015, then the imputed AE onset date will be 15/JAN/2015.
- If both the day and month of the AE onset date are missing but the onset year is equal to the start of study treatment, then the onset date will be replaced by the start of study treatment. For example, if AE onset date is --/---/2014, and study treatment start date is 19/NOV/2014, then the imputed AE onset date will be 19/NOV/2014.
- In all other cases the missing onset day or missing onset month will be replaced by 1.
- Incomplete stop date will be replaced by the last day of the month (if day is missing only), if not resulting in a date later than the date of patient's death. In the latter case the date of death will be used to impute the incomplete stop date.
- In all other cases the incomplete stop date will not be imputed. If stop date of AE is after date of cut-off outcome of AE is ongoing at cut-off.

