8.1.4. Time Period for Collecting AE/SAE Information

The time period for actively eliciting and collecting AEs and SAEs (“active collection period”) for each patient begins from the time the patient provides informed consent, which is obtained before the patient’s participation in the study (ie, before undergoing any study-related procedure and/or receiving investigational product), through and including a minimum of 90 calendar days after the last administration of investigational product.

For patients who are screen failures, the active collection period ends when screen failure status is determined.

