3.5. Safety Endpoints

3.5.1. Adverse Events

Treatment-Emergent Adverse Events

Treatment-emergent adverse events (TEAEs) are those events with onset dates occurring during the on-treatment period for the first time, or if the worsening of an event is during the on-treatment period.

On-treatment period is defined as the time from the first dose of study treatment through minimum (30 days + last dose of study treatment, start day of new anti-cancer drug therapy – 1 day). The start day of new anti-cancer drug therapy after the first dose of study treatment is derived as outlined in [Section 5.2.5](#).

Adverse Events of Special Interest (AESIs)

AESIs are irAE and infusion-related reactions (IRRs). The criteria for classification of an AE as an irAE or IRR are described in [Appendix 1](#) and [Appendix 2](#), respectively.

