5.3.3.4. Date of Start of New Anti-cancer Therapy

Incomplete dates for start date of new anti-cancer therapy (drug therapy, non-drug locoregional therapy, radiation, surgery) will be imputed as follows and will be used for determining censoring dates for efficacy analyses and in the derivation of the end of on-treatment period. PD date below refers to PD date by investigator assessment.

- The end date of new anti-cancer therapy will be included in the imputations for start date of new anti-cancer therapy. If the end date of new anti-cancer therapy is:
 - completely missing then it will be ignored in the imputations below;
 - partially missing with only year (YYYY) available then the imputations below will consider 31DECYYYY as the end date of the new anti-cancer therapy;
 - partially missing with only month and year available then the imputations below will consider the last day of the month for MMMYYYY as the end date of the new anti-cancer therapy.
- For patients who have not discontinued study treatment at the analysis cut-off date, last dose of study treatment is set to the analysis cut-off date in the imputations below.
- If the start date of new anti-cancer therapy is completely or partially missing then the imputed start date of new anti-cancer therapy is derived as follows:

- Start date of new anti-cancer therapy is completely missing

Imputed start date = min [max(PD date + 1, last dose of study treatment + 1), end date of new anti-cancer therapy]

- Only year (YYYY) for start of anti-cancer therapy is available

IF YYYY < Year of min [max(PD date + 1, last dose of study treatment + 1), end date of new anti-cancer therapy] THEN imputed start date = 31DECYYYY;

ELSE IF YYYY = Year of min [max(PD date + 1, last dose of study treatment + 1), end date of new anti-cancer therapy];

THEN imputed start date = min [max(PD date + 1, last dose of study treatment + 1), end date of new anti-cancer therapy];

ELSE IF YYYY > Year of min [max(PD date + 1, last dose of study treatment + 1), end date of new anti-cancer therapy];

THEN imputed start date = 01JANYYYYY.

- Both Year (YYYY) and Month (MMM) for start of anti-cancer therapy are available

IF

YYYY = Year of min [max(PD date + 1, last dose of study treatment + 1), end date of new anti-cancer therapy], AND

MMM < Month of min [max(PD date + 1 day, last dose of study treatment + 1 day), end date of new anti-cancer therapy];

THEN

imputed start date = DAY (Last day of MMM) MMM YYYY;

ELSE IF

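### Three AE onset-date rules ignore the stop date, so an event that ended before first dose can be counted as treatment-emergent

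*SAP*

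**What the plan says.** SAP 5.3.2.2 moves an incomplete AE onset to the start of study treatment in three cases:

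- The date is wholly absent: "If the AE onset date is missing completely, then the onset date will be replaced by the start of study treatment".
- Only the day is absent, and the month and year are those of first dose.
- Day and month are absent, and the year is that of first dose.

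Every other partial onset is handled differently: "In all other cases the missing onset day or missing onset month will be replaced by 1".

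The stop date has its own rule in the same section. A missing day becomes the last day of the month, unless that falls after the date of death, in which case the date of death is used. Any other incomplete stop date is left as it is. The stop date is never compared with onset or with first dose.

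Three further provisions decide what follows:

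- Protocol 8.1.4: active AE collection "for each patient begins from the time the patient provides informed consent", so pre-dose events are in the database.
- SAP 3.5.1: treatment-emergent AEs (TEAEs) "are those events with onset dates occurring during the on-treatment period for the first time", or that worsen in that period. The period opens at first dose (also SAP 5.2.7).
- SAP 6.6.1: AE analyses use TEAEs unless stated otherwise.

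**The concern.** Setting an unknown onset to first dose is a cautious default when the event might have begun on treatment. It stops being cautious when the record itself shows that the event was over before the first dose. Such an event cannot be treatment-emergent and cannot have worsened on treatment, yet the three rules place its onset inside the on-treatment period.

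AEs are part of the primary endpoint, so a misclassified event enters the main safety tables. The record also carries an onset later than its stop.

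Elsewhere the SAP bounds an imputed start by a known end. For new anti-cancer therapy, section 5.3.3.4 says: "The end date of new anti-cancer therapy will be included in the imputations for start date of new anti-cancer therapy". The AE rules have no such bound.

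**Working it through.** **Inputs.** Onset and stop rules from SAP 5.3.2.2; TEAE definition from SAP 3.5.1; planned N = 20 from SAP 5.1.1.

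**Step 1. Reproduce the SAP's own examples.** Applied as written, the rules return both worked examples:

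- "if the AE onset date is --/JAN/2015, and study treatment start date is 15/JAN/2015, then the imputed AE onset date will be 15/JAN/2015"
- "if AE onset date is --/---/2014, and study treatment start date is 19/NOV/2014, then the imputed AE onset date will be 19/NOV/2014"

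**Step 2. Add a stop date before first dose.** Use the same two first-dose dates. An event is a TEAE if imputed onset ≥ first dose. The gap is stop date minus imputed onset.

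| Recorded onset | First dose | Stop date | Imputed onset | Gap (days) | TEAE? |
|---|---|---|---|---|---|
| missing | 15 Jan 2015 | 10 Jan 2015 | 15 Jan 2015 | 10 − 15 = −5 | yes |
| --/Jan/2015 | 15 Jan 2015 | 10 Jan 2015 | 15 Jan 2015 | −5 | yes |
| --/---/2014 | 19 Nov 2014 | 10 Nov 2014 | 19 Nov 2014 | 10 − 19 = −9 | yes |
| --/---/2014 | 19 Nov 2014 | --/Oct/2014, imputed 31 Oct | 19 Nov 2014 | −19 | yes |

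All four events ended before dosing and all four are counted as treatment-emergent.

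**Step 3. Controls, to find where the problem stops.**

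| Recorded onset | First dose | Stop date | Imputed onset | Gap (days) | TEAE? |
|---|---|---|---|---|---|
| --/Jan/2015 | 15 Jan 2015 | --/Jan/2015, imputed 31 Jan | 15 Jan 2015 | 31 − 15 = 16 | yes, no contradiction |
| --/Dec/2014 | 15 Jan 2015 | 10 Jan 2015 | 1 Dec 2014 | 40 | no, correctly |

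A stop day missing in the month of first dose is pushed to month-end, so no conflict arises. A partial onset in an earlier month, with that month recorded, stays before dosing.

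**Step 4. Cap the onset.** Set onset = min(rule date, stop date, including an imputed stop date). The four onsets in step 2 become 10 Jan 2015, 10 Jan 2015, 10 Nov 2014 and 31 Oct 2014, and none is a TEAE. Both controls keep their classification.

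**Step 5. Size per affected patient.** 1/20 = 5.0 percentage points on a preferred-term rate, if that patient has no genuine TEAE under the same term. For a non-serious event this alone reaches the 5% threshold for the table of TEAEs excluding SAEs in SAP 6.6.1.1.

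**Step 6. Where else the imputed onset is used.**

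- *Immune-related events (SAP Appendix 1, step 2):* an onset moved to first dose passes the timing test, though the later steps on treatment and etiology must still be met.
- *Infusion-related reactions (SAP Appendix 2, condition 2):* a negative end-minus-onset difference would satisfy the two-day limit. The required timing entry, during or after infusion, should still screen out pre-dose events.
- *Medications (SAP 5.3.2.3):* the same three patterns and the same gap. Under SAP 6.5.4, a medication that stopped before dosing would move from prior to concomitant.

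**The case against.** The strongest case against is that this will rarely happen and nothing formal depends on it.

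- *Rarity.* A record must combine one of three onset patterns with a stop date before first dose, for an event between consent and dosing. A site that knows when an event ended but not when it began is unusual during prospective collection. This stands. The requirement to start treatment within 3 days (Protocol, Schedule of Activities, note 27) runs from registration, not consent, so it does not by itself bound the pre-dose period.
- *Data cleaning.* SAP section 2 says analyses use cleaned eCRF data, and such a discrepancy would normally be queried. That may remove some records, but neither document specifies an onset-against-stop check, and imputation applies to what cleaning leaves behind.
- *Visibility.* All AEs are listed (SAP 6.6.1) and imputed values are flagged (SAP 5.3.1). A flag in a listing does not take the event out of the TEAE tables.
- *Caution.* The rule errs towards counting events. That is a fair defence for an uncertain event, not for one whose recorded dates rule it out.
- *No decision at stake.* There is no hypothesis test and no decision rule (SAP 5.1.1, 5.1.2). This stands and keeps the point minor.

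A reader might also infer that the contrast with SAP 5.3.3.4 is an internal contradiction. It is not. That section dates a different variable, used for efficacy censoring and the end of the on-treatment period. It shows that the safeguard is available to the sponsor, not that the two sections conflict.

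**Conclusion.** The rule is wrong as written, but the correction is desirable rather than essential. In the three named date patterns, an AE with a recorded or imputed stop date before first dose is classed as treatment-emergent with an onset after its end. Neither document has a provision that prevents it.

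The number of affected records cannot be derived from the documents. An assumed range of 0 to 1 patient in 20 gives 0 to 5 percentage points on a single preferred-term rate.

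Three stronger readings are tempting and are not supported:

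- That every incomplete onset goes to first dose. Other partial dates take day or month 1.
- That the TEAE rates are materially inflated. The count may be zero, and the laboratory abnormalities in the primary endpoint do not depend on AE onset dates.
- That duration summaries are corrupted. No AE table in SAP 6.6.1 to 6.6.4 summarises duration, so negative values would appear mainly in listings.

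**What to change.** Add one sentence to SAP 5.3.2.2:

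> If the AE stop date, complete or as imputed under this section, is earlier than the imputed onset date, the onset date is set to the stop date.

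Apply the same cap to medication start dates in SAP 5.3.2.3.

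The words on imputed stop dates are needed. A cap limited to complete stop dates would miss the fourth case in the working, where a stop of --/Oct/2014 becomes 31 October, before a first dose on 19 November.

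The cost is one sentence in each section and a small programming change. No new data, sample-size change or protocol amendment is needed. There are two limits. The cap relies on the stop date in a record whose onset is already incomplete, so those records should be queried before database release. A stop date with only the year recorded is not imputed under SAP 5.3.2.2, so the cap cannot act on it and a query is the only remedy.

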5.3.2.3. Prior and Concomitant Medications

Incomplete prior/concomitant medication dates will be imputed as follows:

- If the medication date is missing completely, then the medication date will be replaced by the start of study treatment.
- If the day of medication date is missing, but the month and year are equal to the start of study treatment, then the medication date will be replaced by the start of study treatment. For example, if the medication start date is --/JAN/2015, and study treatment start date is 15/JAN/2015, then the imputed medication start date will be 15/JAN/2015.

- If both the day and month of medication start date are missing but the start year is equal to the start of study treatment, then the medication date will be replaced by the start of study treatment. For example, if the medication start date is --/---/2014, and study treatment start date is 19/NOV/2014, then the imputed medication start date will be 19/NOV/2014.
- In all other cases the missing medication day or missing medication month will be replaced by 1.
- Incomplete stop date will be replaced by the last day of the month (if day is missing only), if not resulting in a date later than the date of patient's death. In the latter case the date of death will be used to impute the incomplete stop date.
- In all other cases the incomplete medication stop date will not be imputed.

5.3.2.4. Exposure

No imputation will be done for first dose date. Date of last dose of study drug, if unknown or partially unknown, will be imputed as follows:

- If the last date of study drug is completely missing and there is no End of Treatment eCRF page and no death date, the patient should be considered to be ongoing and use the cut-off date for the analysis as the last dosing date.
- If the last date of study drug is completely or partially missing and there is EITHER an End of Treatment eCRF page OR a death date available (within the cut-off date), then imputed last dose date is:

= 31DECYYYY, if only Year is available and Year < Year of min (EOT date, death date);

= Last day of the month, if both Year and Month are available and Year = Year of min (EOT date, death date) and Month < the month of min (EOT date, death date);

= min (EOT date, death date), for all other cases.

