5.2.7. Definition of On-treatment Period

Safety endpoints will be summarized based on the on-treatment period unless otherwise specified.

On-treatment period is defined as the time from the first dose of study treatment through minimum (30 days + last dose of study treatment, start day of new anti-cancer drug therapy – 1 day).

Safety data collected outside the on-treatment period as described above will be listed and flagged in listings but not summarized.

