YYYY = Year of min [max(PD date + 1, last dose of study treatment + 1), end date of new anti-cancer therapy], AND

MMM = Month of min [max(PD date + 1 day, last dose of study treatment + 1 day), end date of new anti-cancer therapy];

THEN

imputed start date = min [max(PD date + 1 day, last dose of study treatment + 1 day), end date of new anti-cancer therapy];

ELSE IF

YYYY = Year of min [max(PD date + 1, last dose of study treatment + 1), end date of new anti-cancer therapy], AND

MMM > Month of min [max(PD date + 1 day, last dose of study treatment + 1 day), end date of new anti-cancer therapy];

THEN

imputed start date = 01 MMM YYYY;

ELSE IF

YYYY < Year of min [max(PD date + 1, last dose of study treatment + 1), end date of new anti-cancer therapy];

THEN

imputed start date = DAY (Last day of MMM) MMM YYYY;

ELSE IF

YYYY > Year of min [max(PD date + 1, last dose of study treatment + 1), end date of new anti-cancer therapy];

THEN

imputed start date = 01 MMM YYYY.

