6.6.2. Deaths

The frequency (number and percentage) of patients in the safety analysis set who died and who died within 30 days after last dose of study treatment as well as the reason for death, will be tabulated based on information from the ‘Notice of Death’ and ‘Survival Follow-Up’ eCRFs, by treatment group.

- All deaths;
- Deaths within 30 days after last dose of study treatment;

- Reason for Death:
 - Disease progression;
 - Study treatment toxicity;
 - AE not related to study treatment;
 - Unknown;
 - Other.

In addition, date and cause of death will be provided in individual patient data listing together with selected dosing information (study treatment received, date of first/last administration, dose) and will include the following information:

- AEs with fatal outcome (list preferred terms of AEs with outcome=Fatal, as well as AEs of Grade 5),
- Flag for death within 30 days of last dose of study treatment.

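### SAP 5.3.2.4 moves a last dose known to the month to the EOT or death date whenever that date falls in a later calendar year

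*SAP*

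**What the plan says.** The rule in SAP 5.3.2.4 opens with "If the last date of study drug is completely or partially missing and there is EITHER an End of Treatment eCRF page OR a death", the record falling no later than the cut-off. It then gives three results:

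1. Year alone recorded, and earlier: "31DECYYYY, if only Year is available and Year < Year of min (EOT date, death date".
2. Month and year recorded: "Last day of the month, if both Year and Month are available and Year = Year of min (EOT date, death date", with the further condition that the recorded month is earlier than the month of that reference date.
3. Anything else: "min (EOT date, death date), for all other cases".

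SAP 5.3.3.4 imputes the start of new anti-cancer therapy and has a separate branch for a known month in an earlier year. Its condition is "YYYY < Year of min [max(PD date + 1, last dose of study treatment + 1), end date of new anti-cancer therapy", and it returns the last day of the recorded month.

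The imputed date is used in several places. SAP 5.2.7 ends the on-treatment period at "minimum (30 days + last dose of study treatment, start day of new anti-cancer drug therapy – 1 day" and says "Safety endpoints will be summarized based on the on-treatment period unless otherwise specified". SAP 6.6.2 tabulates "Deaths within 30 days after last dose of study treatment". SAP Appendix 1, Table 11, accepts irAEs with onset up to 90 days after last dose. SAP 6.5.3.1 and 6.5.3.2 compute each drug's exposure duration from its own last-dose date. Under SAP 3.4.1, the last dose of the combination is the later of the two drugs' last doses.

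**The concern.** A last dose with month and year recorded, in a year before that of EOT or death, has no line of its own. Line 1 does not apply because the month is known. Line 2 does not apply because the years differ. The catch-all then gives a date that the record itself rules out.

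The result also conflicts with its neighbours. The year-only line respects the recorded year, the same-year line respects the recorded month, and SAP 5.3.3.4 respects the month across a year end. The stop-date rules for adverse events and medications (SAP 5.3.2.2 and 5.3.2.3) also use the last day of the recorded month, limited only by death.

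At stake are the affected drug's exposure figures and, under conditions set out below, the windows behind the primary safety summaries.

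**Working it through.** The plan states no figure to reproduce, so the check applies the three lines exactly as written. The documents contain no patient dates, so all dates below are illustrative. The reference date is the earlier of EOT and death. The excess is the SAP result minus the last day of the recorded period.

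| Recorded last dose | Reference date | Line | SAP result | Last day of recorded period | Excess (days) |
|---|---|---|---|---|---|
| 2018 only | 20 Jan 2019 | 1 | 31 Dec 2018 | 31 Dec 2018 | 0 |
| Oct 2018 | 15 Dec 2018 | 2 | 31 Oct 2018 | 31 Oct 2018 | 0 |
| Dec 2018 | 1 Jan 2019 | 3 | 1 Jan 2019 | 31 Dec 2018 | 1 |
| Dec 2018 | 20 Jan 2019 | 3 | 20 Jan 2019 | 31 Dec 2018 | 20 |
| Dec 2018 | 31 Jan 2019 | 3 | 31 Jan 2019 | 31 Dec 2018 | 31 |
| Nov 2018 | 20 Jan 2019 | 3 | 20 Jan 2019 | 30 Nov 2018 | 31 + 20 = 51 |
| Oct 2018 | 15 Feb 2019 | 3 | 15 Feb 2019 | 31 Oct 2018 | 30 + 31 + 31 + 15 = 107 |

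With EOT on 20 January 2019, a site that records only 2018 gets 31 December 2018. A site that records November 2018 gets 20 January 2019. More information gives a worse date.

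**Is the gap confined to this case?** Take reference dates on the 15th of each month of 2018 and 2019, and every recorded month from January 2017 that is not later than the reference month. That makes 588 combinations. The SAP result falls outside the recorded month in 432, and in all 432 the recorded year is earlier. The other 588 − 432 = 156 are same-year cases and keep their month. This describes the rule; it does not estimate how often patients would be affected.

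**On-treatment period.** For November 2018 with EOT on 20 January 2019, last dose + 30 days is 19 February 2019 as written and 30 December 2018 if the month is kept. This carries over only if the imputed date is the later of the two drugs' last doses (SAP 3.4.1) and no new anti-cancer drug ends the period sooner (SAP 5.2.7).

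**Axitinib exposure.** SAP 6.5.3.2 gives RDI = 100 × cumulative dose / (7 × 2 × 5 × weeks of exposure). Suppose 5 mg BID is taken in full from 1 September to 30 November 2018, the stop is recorded as November 2018, and EOT is 20 January 2019.

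- Recorded month kept: 30 + 31 + 30 = 91 days = 13 weeks; dose 91 × 10 = 910 mg; RDI = 100 × 910 / (70 × 13) = 100%.
- As written, dose from recorded doses only: 91 + 51 = 142 days; denominator 70 × 142/7 = 1,420 mg; RDI = 100 × 910/1,420 = 64.1%.
- As written, dose also accrued to the imputed date: 1,420/1,420 = 100%.

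Duration is overstated by 51 days in both of the last two. RDI is wrong only in the first of them, and SAP 6.5.3.2 does not say which accrual applies. Avelumab dose intensity is built on the start of the last dosed cycle (SAP 6.5.3.1), so only its exposure duration is exposed to this error.

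**The case against.** The best defence is that the gap will seldom bite and would be seen if it did. It needs a missing day, a known month, and EOT or death in a later calendar year, all in one of about 20 patients. Analyses use cleaned eCRF data (SAP 2). Axitinib doses are recorded in a diary (Protocol 5.2) and avelumab is given by site staff, so exact days should usually be recoverable. Imputed dates are flagged in listings (SAP 5.3.1), and the death listing shows last administration beside date of death (SAP 6.6.2). The study is descriptive, with no hypothesis test or decision rule (SAP 5.1). All of this stands as a limit on frequency and consequence. None of it makes the imputed date right.

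It can also be said that the comparison with SAP 5.3.3.4 does not prove an oversight. That is fair. Oversight is the likely explanation, but the point rests on the rule's output and not on intent.

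A reader might infer that partial stop dates are likelier for axitinib because it is taken at home. The documents do not show this; a dose-by-dose diary is also a source for the exact day.

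**Conclusion.** The rule is wrong as written for one class of partial dates, and no other section covers that class. In the ordinary case, a December last dose with a January EOT or death, the error is 1 to 31 days. It grows only with the distance to EOT or death. The affected drug's exposure duration is overstated every time. The effect on axitinib RDI depends on how cumulative dose is accrued. The effects on treatment-emergent events, 30-day deaths and the irAE window depend on which drug ended later; new anti-cancer drug therapy can cap the on-treatment period but not the irAE window. Few patients, perhaps none, would be affected.

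A reader might go further and picture a last dose in October 2017, no EOT page and death on 15 March 2018: an error of 30 + 31 + 31 + 28 + 15 = 135 days, a death wrongly counted within 30 days, every intervening event made treatment-emergent, and, after 182 days of full dosing, an RDI of 182/(182 + 135) = 57%. The documents do not support this as the expected consequence:

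- It requires that no EOT record exists; an EOT dated before death would cap the error.
- Events to 30 November lie within 30 days of 31 October and count in any case.
- Active AE collection is required only to a minimum of 90 days after last dose (Protocol 8.1.4), here 29 January 2018, and recording of non-serious events stops at new anti-cancer therapy (Protocol 8.1.4.2).
- If avelumab ended later than October, part or all of the shift in the safety windows disappears.
- The 57% holds dose fixed while extending duration.

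One patient is 1/20, or 5 percentage points, of any safety table. That is true of any misclassified patient and says nothing about how likely this one is.

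**What to change.** Replace the second line of SAP 5.3.2.4 with: *Last day of the recorded month, when month and year are both recorded and that year-month is earlier than the year-month of min (EOT date, death date).* Keep the catch-all for the remaining cases.

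The new line can never give a date after EOT or death, because the recorded month ends before the reference month begins. It leaves every same-year, year-only and fully missing case as it is now, and brings the section into line with SAP 5.3.3.4. The cost is one line of text and the matching line of derivation code, with no new data needed.
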